8.3 Sample size calculations for immunogenicity (Part B)

Immunogenicity sample size calculations allow for a 10% rate of missing immunogenicity data at Months 2.5 and 6.5 ($n = 18$ for analysis) and 15% rate of missing immunogenicity data at Months 12 and 18 ($n = 17$ for analysis).

The first goal is to evaluate immune response rates based on data from the primary TZM-bl neutralizing antibody assay among vaccinees. The precision with which the true response rate can be estimated from the observed data depends on the true underlying response rate and the sample size. Two-sided 95% confidence intervals for the response rate based on observing a particular response rate among vaccinees is shown in Table 4. Calculations are done using the score test method [1].

Table 4: Two-sided 95% confidence intervals for the true response rate based on observing a particular response rate among vaccinees ($n = 18$)

No. of responses	Observed response rate (%)	95% confidence interval
4/18	22.2	(9.0, 45.2)
6/18	33.3	(16.3, 56.3)

8/18	44.4	(24.6, 66.3)
10/18	55.6	(33.7, 75.4)
12/18	66.7	(43.7, 83.7)
14/18	77.8	(54.8, 91.0)
15/18	83.3	(60.8, 94.2)
16/18	88.9	(67.2, 96.9)
17/18	94.4	(74.2, 99.0)

As shown in Table 5, there is limited power for a formal comparison of immunogenicity response rates between vaccine arms of size $n = 20$. For either 80% or 90% power, the sizes of differences that the trial is powered to detect are large. These calculations use a Fisher's exact 2-sided test with a Type I error rate of 0.05. However, the study is adequately powered to detect the differences seen in the CAVD 641 study in rhesus macaques by [name]. Rates of autologous tier 2 neutralizing antibody responses at week 26 (the peak timepoint) were compared between arms with Alum-3M-052 or GLA-LSQ adjuvant, both with BG505-SOSIP protein. The large difference in response rates – 50% vs. 100% – could be detected with 97% power.

Table 5: Power for comparison of response rates between 2 arms (n1 = 18, n2 = 18)

True response rate Arm 1 (%)	Minimum true response rate in Arm 2 in order to detect a difference	
	80% power	90% power
10	58	65
20	71	77
30	81	87
40	89	94
50	95	99

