Some immunologic assays have underlying continuous or count-type readout that are dichotomized into responder/nonresponder categories (e.g., intracellular cytokine staining). If treatment arm differences for these assays are best summarized by a mixture model, then either Lachenbruch's test statistic [4] or an alternative two-part test [5] will be used to evaluate the composite null hypothesis of equal response rates in the 2 arms and equal response distributions. Lachenbruch's test statistic equals the square of a binomial Z-statistic for comparing the response rates plus the square of a Wilcoxon statistic for comparing the response distributions in the subgroup of responders. A permutation procedure is used to obtain a 2-sided p-value. For estimation, differences in response rates between arms will be estimated using the methods described above, and in the subgroup of positive responders, differences in location parameters between arms will be estimated using the methods described above.

More sophisticated analyses employing repeated measures methodology (for example, linear mixed models or marginal mean models fit by generalized estimating equations) will be utilized to incorporate immune responses over several timepoints and to test for differences over time and differences in trajectories across treatment arms. For example, repeated measures analyses will be conducted to evaluate trajectories in innate immune response over Days 1, 3, 7 relative to responses measured at Day 0. However, inference from such analyses would be limited by the small sample size of this study. All statistical tests will be 2-sided and will be considered statistically significant if $p \leq 0.05$.

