Based upon previous HVTN trials, missing 10% of immunogenicity results for a specific assay is common due to study participants terminating from the study early, problems in shipping specimens, or low cell viability of processed PBMCs. To achieve unbiased statistical estimation and inferences with standard methods applied in a complete-case manner (only including participants with observed data in the analysis), missing data need to be missing completely at random (MCAR). Following the most commonly used definition, MCAR assumes that the probability of an observation being missing does not depend on any participant characteristics (observed or unobserved). When missing data are minimal (specifically if no more than 20% of participants are missing any values), then standard complete-case methods will be used, because violations of the MCAR assumption will have little impact on the estimates and hypothesis tests.

If a substantial amount of immunogenicity data are missing for an endpoint (at least 1 value missing from more than 20% of participants), then using the methods that require the MCAR assumption may give misleading results. In this situation, analyses of the immunogenicity endpoints at a specific timepoint will be performed using generalized linear models fit by maximum likelihood. These methods provide unbiased estimation and inferences under the parametric modeling assumptions and the assumption that the missing data are missing at random (MAR). MAR assumes that the probability of an observation being missing may depend upon the observed responses and upon observed covariates, but not upon any unobserved factors. Generalized linear models for response

rates will use a binomial error distribution and for quantitative endpoints, a normal error distribution. For evaluating repeated immunogenicity measurements over time, linear mixed effects model will be used. If the immunological outcomes are left- and/or right-censored, then the linear mixed effects models of Hughes [6] will be used, because they accommodate the censoring. In addition, secondary analyses of repeated immunogenicity measurements may be done using weighted generalized estimating equation (GEE) [7] methods, which are valid under MAR. All of the models described above in this paragraph will include as covariates all available baseline predictors of the missing outcomes.

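### The SAP allows GEE tests of trajectory differences at p ≤ 0.05 with about 9 to 20 participants per arm and names no small-sample form

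*SAP*

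**What the plan says.** Section 9.4.1 plans repeated-measures analyses by, for example, "linear mixed models or marginal mean models fit by generalized estimating equations) will be utilized to incorporate immune responses over several timepoints". Their purpose is "to test for differences over time and differences in trajectories across treatment arms". The example given is to "evaluate trajectories in innate immune response over Days 1, 3, 7 relative to responses measured at Day 0". A caveat follows: "inference from such analyses would be limited by the small sample size of this study". The next sentence makes every test two-sided with significance at p ≤ 0.05.

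Three other places bear on the choice of method:

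- **Section 9.4.1, missing data.** When more than 20% of participants lack at least one value, repeated measurements go to a linear mixed model. Secondary analyses may then use "weighted generalized estimating equation (GEE) [7] methods, which are valid under MAR".
- **Section 11.5 (Trucount).** A linear mixed model is fixed, with a random subject effect, Group, Day as a factor and their interaction.
- **Section 9.4.1, comparisons at one timepoint.** Response rates are compared by Barnard's test, and magnitudes by a Wilcoxon or t test.

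Sections 8.3 and 8.5 give the numbers expected for analysis: 18 per Part B arm at Months 2.5 and 6.5, 17 at Months 12 and 18, and 9 per Part C arm.

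**The concern.** The GEE sandwich variance is a large-sample estimator. With few participants per arm it is too small on average and is itself imprecise. A chi-square reference ignores both problems, so the test rejects too often, and the excess grows with the degrees of freedom. A mixed model with an F reference does not have this problem to the same degree. The SAP offers both methods for the same hypothesis without choosing, so the real type I error of a trajectory claim depends on which one the analyst picks and on the software default.

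At stake are claims that adjuvants differ in kinetics, for the readouts left to the open choice. These are the RNAseq and serum cytokine innate endpoints, and neutralization, BAMA and B-cell trajectories when the 20% missing-data rule is not triggered. The small-sample caveat does not say that a reported p of 0.05 may not correspond to 5%.

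**Working it through.** **Inputs from the SAP.** Expected n: 20 × 0.90 = 18 and 20 × 0.85 = 17 (Part B), and 10 × 0.90 = 9 (Part C). These match sections 8.3 and 8.5. Part B has four vaccine arms. There are four visits, either Days 0, 1, 3, 7 or Months 2.5, 6.5, 12, 18. The level is 0.05. The SAP states no error rate for these tests beyond the nominal level, so there is no figure of its own to reproduce.

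**Assumptions, not in the SAP.** Uncorrected sandwich variance, Wald chi-square reference, a separate mean for each arm and visit, normal outcomes, complete data, within-person correlation 0.5.

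**Two arms of equal size n: exact result.** Under these assumptions the GEE estimates are the cell means, and each arm's covariance is estimated with divisor n instead of n − 1. For q contrasts, the Wald statistic is W = n/(n − 1) × T², where T² is Hotelling's statistic with ν = 2(n − 1). Hence

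false-positive rate = P( F(q, ν − q + 1) > χ²(0.95, q) × (n − 1)/n × (ν − q + 1)/(qν) ).

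- n = 9, q = 3: 7.815 × 8/9 = 6.946; × 14/48 = 2.026; P(F(3, 14) > 2.026) = 15.7%.
- n = 17, q = 3: 7.815 × 16/17 = 7.355; × 30/96 = 2.298; P(F(3, 30) > 2.298) = 9.8%.
- n = 9, q = 1 (slope): 3.841 × 8/9 = 3.415; P(F(1, 16) > 3.415) = 8.3%.
- n = 17, q = 1: 3.841 × 16/17 = 3.615; P(F(1, 32) > 3.615) = 6.6%.

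**Simulation, 20,000 null datasets per setting, four visits, nominal 5%.**

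| Comparison | Omnibus | Linear slope |
|---|---|---|
| 9 v 9 | 15.7% | 8.3% |
| 10 v 10 | 14.0% | 7.9% |
| 9 v 18 (Part C v Part B) | 14.0% | 8.0% |
| 17 v 17 | 9.9% | 6.7% |
| 18 v 18 | 9.6% | 6.7% |
| 20 v 20 | 9.0% | 6.7% |
| four arms of 17 | 17.2% | 9.1% |
| four arms of 18 | 16.4% | 8.9% |
| four arms of 20 | 15.2% | 8.1% |

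The pairwise rows agree with the exact formula to within simulation error. With three visits the omnibus rates fall to 11.6% (9 v 9), 8.0% (18 v 18) and 11.8% (four arms of 18). Heavy-tailed (t with 5 df) or AR(1) data change the four-visit results by about 1 point or less. A smaller check with a packaged GEE routine (1,200 to 1,500 datasets) gave 14.0% (9 v 9), 9.9% (18 v 18), 15.5% (four arms of 18) and 12.8% (four arms of 20).

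**Binary responses.** A logit check (latent correlation 0.5, response 50-70%, datasets without empty or full cells) gave 7-9% (9 v 9), 7% (17 v 17) and 9-10% (four arms of 17).

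**Candidate remedies, same settings.**

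- Compound-symmetry mixed model with F test: 3.6% to 5.4% (Monte Carlo SE about 0.6 points).
- Mancl-DeRouen variance, chi-square reference kept: 9.7% (9 v 9), 6.9% (18 v 18), 11.4% (four arms of 18). Correcting the variance alone is not enough.
- Mancl-DeRouen variance with F reference: 5.2% (9 v 9) and 5.0% (17 v 17), but 8.5% (four arms of 17). It suits pairwise contrasts, not the multi-arm omnibus test.
- F test with unstructured covariance pooled over arms: 4.8% to 5.1% when the arms share a covariance. At 9 v 18 with twice the SD in the smaller arm (an assumption), two runs gave 17.0% and 17.7%; with the SDs reversed, 1.6% and 1.4%. Pooling is therefore unsafe for unequal arms with unequal variances.

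**The case against.** The strongest reply is that the SAP never says that an uncorrected sandwich or a chi-square reference will be used. That is true. The rates above describe a common default, not a stated plan. What stands is that nothing in the SAP excludes that default.

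Second, the mixed model is already the named method in two places, and this narrows the point. Trucount is settled by section 11.5. For Part B durability over four visits, the 20% rule may well apply. If missingness were independent across visits, 1 − 0.90² × 0.85² = 41% of participants would lack at least one value; if fully nested, 15%. Weighted GEE is then only an optional secondary analysis, and the remark on its validity concerns the missing-data mechanism, not finite-sample error. If the rule is not triggered, and for RNAseq and cytokine trajectories, the choice remains open.

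Third, a reader might infer that the durability objectives rest on this test. They do not. Their endpoints are rates and magnitudes at stated visits, tested per timepoint, and Table 6 sizes the durability comparison by the Wilcoxon test.

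Fourth, a reader might take 15-18% as the rate for 9 to 20 per arm in general. The figures do not support that. Rates near 15-17% belong to the four-arm omnibus test and to the 9 v 9 omnibus test. Part B pairs run at 10% or less, and the SAP does not itself specify a four-arm omnibus test.

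The caveat about small samples is fair warning on precision, but it specifies no method. Elsewhere the same section does specify small-sample methods: Barnard's test and a permutation p-value for the two-part test.

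**Conclusion.** The point holds in limited form. Where the SAP leaves the repeated-measures method open, GEE at p ≤ 0.05 is permitted without a small-sample form. Under the usual uncorrected default, with continuous outcomes and four visits, the false-positive rate is roughly 7-10% for a Part B pair, 8-16% for 9 v 9 in Part C, and 15-17% for the four-arm Part B omnibus test. Fewer visits or binary responses lower the omnibus figures. More arms or visits raise them: 27.1% with four arms of 18 plus the 8 pooled placebo recipients, and 26.0% with four arms of 20 at six visits.

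These figures rest on complete, normal data and on an assumed variance estimator and reference distribution. They do not apply to Trucount, to the mixed-model branch for missing data, or to the per-timepoint tests.

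**What to change.** Add to section 9.4.1:

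- **Quantitative trajectories:** a linear mixed model with Kenward-Roger F tests as the method. Allow arm-specific covariance where variances differ, especially for unequal arms such as Part C versus Part B. Kenward-Roger with arm-specific covariance was not simulated here; with 9 in an arm it is still an approximation, and a check by simulation before use is sensible.
- **GEE or weighted GEE, for example for binary responses:** replace the default Wald chi-square. For pairwise contrasts, use the Mancl-DeRouen variance with an F or t reference. For multi-arm omnibus tests, permute arm labels among participants, provided that missingness and variance are similar across arms.

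The cost is a few sentences and a software option. GEE p-values will be somewhat larger. No new data or participants are needed.

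### Above 20% missing, the single-timepoint GLM with baseline covariates does not have the MAR validity the SAP claims, and the 20% rule ignores imbalance between arms

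*SAP*

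**What the plan says.** SAP section 9.4.1 first states that complete-case methods need data missing completely at random. It then sets a threshold for small missingness, worded as "specifically if no more than 20% of participants are missing any values". Up to that threshold the plan's rule and its reason are: "then standard complete-case methods will be used, because violations of the MCAR assumption will have little impact on the estimates and hypothesis tests". No calculation, reference or per-arm condition goes with this.

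Where missingness is larger ("at least 1 value missing from more than 20% of participants"), the plan changes method: "analyses of the immunogenicity endpoints at a specific timepoint will be performed using generalized linear models fit by maximum likelihood". The SAP says these methods are unbiased if the parametric model is right and the data are MAR. It defines MAR so that missingness may depend on observed responses as well as on observed covariates. The paragraph ends: "All of the models described above in this paragraph will include as covariates all available baseline predictors of the missing outcomes".

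The same paragraph names a linear mixed model, a censored-data version of it, and optional weighted GEE. It assigns all of these to repeated measurements over time. Earlier in section 9.4.1, repeated-measures models are also planned for trajectories, with no missingness threshold. The primary neutralization endpoints for Parts B and C (sections 3.2.1 and 3.3.1) are set at fixed timepoints, 2 weeks after the second and third vaccinations.

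**The concern.** A GLM for one timepoint has one outcome per participant. A participant without that outcome contributes nothing to the likelihood, so maximum likelihood here is a covariate-adjusted complete-case analysis. With only baseline predictors in the model, the participant's earlier post-vaccination titre is never used. The claimed validity therefore does not cover the observed-responses part of the SAP's own MAR definition. If low early responders were lost more often, and more often in one arm, the fallback would keep most of the bias while being reported as free of it.

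Below the threshold, the assertion of little impact is meant to justify complete-case tests. Because the 20% is counted over participants and not within arms, it places no limit on imbalance, and imbalance is what biases an arm contrast.

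**Working it through.** **The plan's own figures.** Section 8.3 allows 10% missing at Months 2.5 and 6.5 and 15% at Months 12 and 18: 20 x 0.90 = 18 and 20 x 0.85 = 17 per arm. Simulating the one-sided 0.025 Wilcoxon test at a 1.0 SD difference gives power of 80.7% and 78.3%, against 81% and 78% in Table 6. These reproduce. They price the loss of numbers only; the SAP gives no figure for bias.

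**Assumptions not in the documents.** Logistic missingness with slope -1 or -2 in log odds per SD of the earlier response; correlation between visits 0.5 to 0.8; correlation of the baseline covariate with response 0.2 or 0.5.

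**Bias in one arm's mean.** If loss depends on the earlier titre, the bias at the later visit is the visit correlation times the shift in mean earlier titre among those retained. At slope -1 and correlation 0.6 to 0.8:
- 20% missing: 0.10 to 0.14 SD.
- 25% missing: 0.13 to 0.17 SD (0.22 SD at slope -1.5, correlation 0.8).

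These are complete-case values. They carry over to the GLM when its baseline covariates say little about the earlier titre.

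**Bias in the arm contrast, GLM rule in force.** No true difference, 20 per arm, slope -2, visit correlation 0.7, covariate correlation 0.2:

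| Missing by arm | Complete-case bias | GLM bias | GLM type I error | Likelihood using the earlier response, bias |
|---|---|---|---|---|
| 50%/0% (25% overall) | 0.42 SD | 0.41 SD | 16.6% | 0.00 SD |
| 40%/20% (30% overall) | 0.16 SD | 0.15 SD | 7.2% | about 0.01 SD |

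At 50%/0%, the GLM bias runs from 0.28 to 0.46 SD over visit correlations 0.5 to 0.8. It falls to 0.28 SD at visit correlation 0.7 if the covariate correlation is 0.5. If missingness depends only on the included baseline covariate, the GLM bias is about 0.00 SD.

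**The rule at or below 20%.** Part B has 4 x 20 = 80 vaccinees, and 20% of 80 is 16. All 16 could come from one arm (16/20 = 80% of it) and the rule would still be met. In a two-arm comparison, 40%/0% is (8 + 0)/40 = 20%. Type I error of the complete-case t-test at a nominal 5%, visit correlation 0.7:
- 20%/20%: near 5% at either slope.
- 30%/10%, slope -2: 7%, bias 0.16 SD.
- 40%/0%, slope -1: about 9% (8 to 11% over correlations 0.6 to 0.8).
- 40%/0%, slope -2: about 14 to 15%, bias 0.35 SD.

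**Response rates.** With 4 of 20 missing and a true rate of 10/20, the observed rate lies between (10 - 4)/16 = 37.5% and 10/16 = 62.5%. With 2 missing it lies between 8/18 = 44% and 10/18 = 56%.

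**When the trigger fires at the planned rates.** The lower end assumes the same people are missing each time, the upper end independent visits:
- Two primary neutralization visits: 10% to 1 - 0.9^2 = 19%.
- Two neutralization durability visits: 15% to 1 - 0.85^2 = 28%.
- All four visits (binding antibody, memory B cell and ICS endpoints): 15% to 1 - 0.9^2 x 0.85^2 = 41%.

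**The case against.** Four stronger readings are tempting, and the SAP does not support them.

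- *A reader might infer that the plan ignores earlier responses altogether.* It does not. Section 9.4.1 plans mixed models and allows weighted GEE for repeated measurements, and these can use earlier responses. The gap is that they are assigned to trajectories and not to the timepoint contrasts.
- *A reader might take the 41% to mean the primary endpoint will go to the GLM.* The trigger is set for an endpoint. At the planned rates the two-visit primary endpoint stays at 10 to 19%, under the threshold. Which visits are counted matters mainly for the durability and four-visit secondary endpoints.
- *A reader might infer that adjuvant reactogenicity will cause unequal drop-out.* The SAP gives no drop-out by arm. It attributes missing results to early termination, shipping and low cell viability, and it analyses participants regardless of injections received, so stopping vaccination does not by itself remove them.
- *A reader might conclude that complete-case analysis should be abandoned.* With equal loss the contrast is close to unbiased. At the expected 10%, one arm's mean is off by about 0.06 to 0.07 SD at slope -1. The standard error of a difference with 16 per arm is sqrt(2/16) = 0.35 SD, and the trial is powered for 1 SD. The response-rate bounds are extremes and lie inside the score interval for 8/16 (28 to 72%).

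These points limit the size of the problem. They do not repair the MAR statement for the GLM, nor do they supply a per-arm condition for the 20% rule.

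**Conclusion.** The point holds in limited form. The claim that the timepoint GLM is unbiased under MAR, as the SAP defines MAR, is wrong whenever missingness depends on earlier responses. It is right only when missingness depends on the baseline covariates in the model. Each arm's mean is then biased by 0.13 to 0.17 SD at 25% missing under the slope -1 mechanism, and the contrast is biased to the extent that loss differs between arms.

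The assertion of little impact up to 20% is unsupported because the rule has no per-arm limit. At a 40%/0% split, type I error is about 9% (slope -1) to 14% (slope -2) at correlation 0.7; with equal loss it is near 5%. All sizes rest on assumed correlations and missingness slopes, and the large ones need a split far more uneven than anything the SAP expects. That the GLM fails to use earlier responses does not depend on those assumptions. This should be corrected, but it does not undermine the main analysis when loss is low and balanced.

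**What to change.** 1. Above the threshold, take the timepoint contrasts from the linear mixed model already cited, or its censored version, fitted over the available visits. Use weighted GEE for response rates. Enter earlier responses as joint outcomes; adding them to the GLM as covariates would condition on a post-vaccination response and change the contrast. Alternatively, keep the GLM and restrict its MAR claim to missingness that depends on the included baseline covariates.
2. Apply the 20% rule per arm and per endpoint visit, and say which visits count.
3. Replace the assertion of little impact with a statement that complete-case tests are the main analysis when missingness is low and balanced between arms.
4. Add best-case and worst-case bounds for the primary response rates as a sensitivity analysis at any level of missingness. A MAR model does not cover loss that depends on the unobserved value itself.

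The cost is SAP wording and modest programming of models already named. The downsides are reliance on a parametric model at about 20 per arm and possible separation in a response model if an arm reaches 100%, which is one side of the 50% versus 100% planning case in section 8.3. There is also no gain for neutralization at week 10: section 11.3 commits Part B only to weeks 10 and 26 and leaves baseline and later visits to discretion, so only week 26 has a committed earlier titre.
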